8. SELECTION AND WITHDRAWAL OF PATIENTS

8.1. Patient Eligibility Criteria

To be eligible to participate in this trial, patients must meet all of the following criteria:

1. Completed one of the parent trials
2. Does not have a condition that would require withdrawal from one of the parent trials
3. Has no conditions requiring treatment with a prohibited concomitant medication
4. Is not receiving treatment with any of the following drugs or interventions within the corresponding timeframe:
 - At Baseline (Day 1)
 - CYP2C8 inhibitors (eg, gemfibrozil or clopidogrel) or inducers (eg, rifampicin)

Two weeks prior to Baseline (Day 1)

- Monoamine oxidase inhibitors (eg, selegiline, phenelzine)
5. Ability to provide written informed consent and to be compliant with the schedule of protocol assessments
 6. Female patients of childbearing potential:

Must agree to practice a highly effective method of contraception throughout the study until completion of the 90-Day Safety Follow-up Visit. Highly effective methods of contraception are those that alone or in combination result in a failure rate of a Pearl index of less than 1% per year when used consistently and correctly.

Acceptable methods of birth control in this study are the following:

- combined hormonal (oestrogen and progestogen containing) contraception, which may be oral, intravaginal, or transdermal
- progestogen-only hormonal contraception associated with inhibition of ovulation, which may be oral, injectable, or implantable
- placement of an intrauterine device (IUD)
- placement of an intrauterine hormone-releasing system (IUS)
- bilateral tubal occlusion
- vasectomised partner
- sexual abstinence.

All patients:

Periodic abstinence (calendar, symptothermal, post-ovulation methods), withdrawal (coitus interruptus), spermicides only, and lactational amenorrhoea method (LAM) are

not acceptable methods of contraception. Female condom and male condom should not be used together.

8.2. Patient Withdrawal Criteria

Reasons for patient withdrawal from the trial include, but are not limited to the following:

- Investigator decision: The Investigator may withdraw the patient from the trial if it is determined that it is not safe or is not in the patient's best interest to receive further treatment with RPC1063. The Medical Monitor should be promptly notified of the decision.
- Noncompliance with investigational drug: After consultation between the Investigator, the Medical Monitor, and the Sponsor when appropriate, a patient may be withdrawn from the trial for failure to comply with dosing regimen as specified by the protocol.
- Intercurrent illness: A patient may be withdrawn from the trial if, in the judgment of the treating Investigator, the patient develops an intercurrent illness or complication that is not consistent with the protocol requirements or that, in any way, justifies withdrawal.
- Adverse event: A patient must be withdrawn from the trial if, in the judgment of the Investigator or if specified in the protocol, the patient develops an AE such as an intercurrent illness or complication that justifies withdrawal.
- Lack of efficacy: Decision by the patient and/or the Investigator to withdraw the patient from the trial due to a lack of expected or desired effect related to a therapy.
- Withdrawal of Consent: The patient may choose to withdraw from the trial at any time. Every effort should be made within the bounds of safety and patient choice to have each patient complete the Early Termination Visit and the 28-Day and 90-Day Safety Follow-up Visits. If a patient withdraws consent, the only additional investigational data to be collected will be the follow up of SAEs as mandated by the protocol.
- Pregnancy: If the patient becomes pregnant, the patient must be withdrawn from the trial (see also Section 12.4.5)
- Trial termination by Sponsor
- Other

All patients who withdraw from the trial should complete an Early Termination Visit. Patients should be instructed to contact the Investigator (e.g. by phone) if they plan to withdraw from the study to discuss study drug discontinuation plans, and schedule the dependence and withdrawal assessment visits. Central laboratory testing of ALC will continue every 14 days (\pm 3 days) after discontinuation of RPC1063 or the End of Treatment/Early Termination Visit until ALC is above the lower limit of normal or until the Investigator is notified to discontinue (Section 12.2.1). Patients should be encouraged to complete the ALC and Safety Follow-up Visits for the

collection of safety data, including lymphocyte recovery, PK sampling, and to assess their disease status. Treatment for MS can be started after the 28-Day Safety Follow-up Visit based on Section 9.5.

The reason for withdrawal from the trial will be recorded in the clinical records and the patient's electronic case report form (eCRF). For those patients whose status is unclear because they fail to appear for trial visits without stating an intention to withdraw from trial participation, the Investigator should document in the source documents the steps taken to contact the patient (eg, dates of telephone calls, registered letters) prior to withdrawing the patient from the trial.

9. TREATMENT

9.1. Treatments Administered

The Investigator must ensure that RPC1063 will be used only in accordance with the protocol.

Initial investigational drug treatment will consist of a 7-day dose escalation regimen, as applicable, of RPC1063 0.25 mg (equivalent to ozanimod 0.23 mg) on Days 1 to 4, RPC1063 0.5 mg (equivalent to ozanimod 0.46 mg) on Days 5 to 7, and RPC1063 1 mg (equivalent to ozanimod 0.92 mg) from Day 8 onward. Patients from either the blinded extension of the RPC01-201 Part A trial or the RPC01-1001 trial will not require initial dose escalation unless the duration between the last dose of RPC1063 in the parent trial and the first dose in RPC01-3001 is more than 14 days. Patients will receive RPC1063 at 1 mg/day until the end of the trial or until the Sponsor discontinues the development program.

In the event that commercial ozanimod or an access program becomes available prior to December 2022, subjects may transition to the commercial product after discussion with the Investigator at his/her discretion. Subjects who transition to commercial ozanimod are not required to attend safety follow-up visits after their end of treatment visit as long as commercial ozanimod is started within 14 days of discontinuation of study drug. Otherwise, all other subjects continuing in the study and subsequently discontinuing prior to the availability of commercial ozanimod in their country/state or by end of the study will be required to follow the schedule of assessments through the safety follow up visits.

9.2. Selection of Dose in the Trial

The dose of 1 mg RPC1063 is the higher of the two doses (0.5 and 1 mg) that demonstrated clinically meaningful and statistically significant efficacy in the Phase 2 and Phase 3 RMS trials. To date, the 2 doses have a comparable safety profile.

By assigning all patients to the 1 mg dose, this trial will collect safety data that would support marketing applications for both doses.

9.3. Selection and Timing of Dose for Each Patient

Patients will self-administer RPC1063 by mouth once per day. Patients should be instructed to take RPC1063 at approximately the same time each day with or without food.

9.3.1. Instructions for Missed Dose(s) of RPC1063 Capsules

Patients should be instructed that if they forget to take a dose, they can take the dose within 4 hours of the normal dosing time; otherwise they should take their next dose at the regular time on the following day. If the patient vomits the capsule, he/she should be instructed not to take another capsule on the same day, but to take the next dose at the regular time on the following day. Patients will record missed doses in a diary that will be reviewed at every visit by site staff and the site monitor.

If a patient misses a dose during dose escalation, the Medical Monitor should be contacted to discuss completing the dose escalation schedule.

If the patient misses more than 7 consecutive doses for any reason, Day 1 cardiac monitoring procedures will be performed on the first day that the patient resumes dosing. If the patient misses more than 14 consecutive doses for any reason, the Medical Monitor must be contacted to discuss procedures for resuming therapy, which will include an additional dose escalation schedule.

9.4. Treatment of Relapses

Patients who experience a relapse may receive treatment with intravenous (IV) corticosteroids, if judged to be clinically appropriate by the Investigator. The following standard treatment regimen should be used: as warranted, up to 1.0 g IV methylprednisolone per day for a maximum of 5 consecutive days. Any other medications or deviation from the allowed IV methylprednisolone treatment should be discussed with the Medical Monitor.

A patient who experiences a relapse after completing a parent trial, but prior to entering RPC01-3001, may receive the IV methylprednisolone treatment regimen.

9.5. Concomitant Medications

All treatments, other than RPC1063, being taken by the patients on entry to the trial or at any time during the trial, including through the 90-Day Safety Follow-up Visit, are regarded as concomitant treatments and must be documented on the appropriate section of the eCRF.

Treatment for symptoms related to MS (eg, spasticity, incontinence, pain, fatigue, and depression) is not restricted, but Investigators should attempt to keep therapies or treatments reasonably constant throughout the trial. Changes may be made if appropriate for a patient's well-being in the clinical judgment of the treating Investigator.

Administration of concomitant medications must be reported in the appropriate section of the eCRF along with dosage information, dates of administration, and reasons for use. For medications with a single active ingredient, generic names for concomitant medication should be used, if possible. For combination products, brand names should be used. The total daily dose should be filled in whenever possible.

9.5.1. Concomitant Medications Prohibited Through the 28-Day Safety Follow-up Visit

The following medications cannot be used during the trial through the 28-Day Safety Follow-up Visit:

- Any approved and unapproved disease-modifying MS agents
- Treatment with Class Ia or Class III anti-arrhythmics (examples of prohibited systemic cardiac medications are provided in [Table 5](#)) or treatment with a combination of 2 or more agents known to prolong PR interval (eg, combination of a beta blocker and verapamil) are prohibited during the study unless approved by the Sponsor's representative. (Note that [Table 5](#) does not provide a comprehensive list. The Medical Monitor should be contacted for further guidance if needed).

- Systemic corticosteroid therapy or ACTH, except for treatment of protocol-defined treatment of relapses. Corticosteroids that are by non-systemic routes (eg, topical, inhaled, intra-articular) are allowed.
- Live or live attenuated vaccines
- Intravenous immunoglobulin (IVIg) or plasmapheresis
- Immunosuppressive agents that deplete lymphocytes
- Breast cancer resistance protein (BCRP) inhibitors (eg, cyclosporine, eltrombopag)
- Monoamine oxidase inhibitors (eg, selegiline, phenelzine)
- CYP2C8 inhibitors (eg, gemfibrozil and clopidogrel) or inducers (eg, rifampicin)

For patients who are currently enrolled and are receiving BCRP inhibitors, monoamine oxidase inhibitors or CYP2C8 inhibitors or inducers, an individual safety assessment will be conducted and, if indicated, either the concomitant medication will be discontinued and the patient will continue in the study or investigational drug will be discontinued and the patient will be withdrawn from the study.

Table 5: Examples of Prohibited Cardiac Medications (Systemic Use)

Pharmaceutical Class	Example Medications
Class Ia or Class III Anti-arrhythmic drugs	amiodarone, bepridil hydrochloride, disopyramide, dofetilide, dronedarone, flecainide, sotalol, ibutilide, lidocaine, procainamide, propafenone, quinidine, tocainide

9.5.2. Concomitant Medications Between the 28-Day Safety Follow-up Visit and the 90-Day Safety Follow-up Visit

Interferon- β and glatiramer acetate may be started after the 28-Day Safety Follow-up Visit at the Investigator's discretion.

Certain disease-modifying MS agents, lymphocyte-trafficking inhibitors (eg, fingolimod, natalizumab) or immunosuppressive agents that deplete lymphocytes (eg, ocrelizumab, cladribine, alemtuzumab) may be used in consultation with the Medical Monitor between the 28-Day Safety Follow-up Visit and the 90-Day Safety Follow-up Visit.

The following medications should not be used without consultation with the Medical Monitor between the 28-Day Safety Follow-up Visit and the 90-Day Safety Follow-up Visit:

- Treatment with Class Ia or Class III anti-arrhythmics (examples of prohibited systemic cardiac medications are provided in [Table 5](#)) or treatment with a combination of 2 or more agents known to prolong PR interval (eg, combination of a beta blocker and verapamil) are prohibited during the study unless approved by the Sponsor's representative. (Note that [Table 5](#) does not provide a comprehensive list. The Medical Monitor should be contacted for further guidance if needed).

- Live or live attenuated vaccines
- Monoamine oxidase inhibitors (eg, selegiline, phenelzine)
- CYP2C8 inhibitors (eg, gemfibrozil and clopidogrel) or inducers (eg, rifampicin)

9.6. Treatment Compliance

It is the Investigator's responsibility to ensure that patients are correctly instructed on how to take their investigational drug and that each patient is fully compliant with their assigned dosage regimen. Records of investigational drug used and intervals between visits will be kept during the trial. Drug accountability will be noted by the site monitor during site visits and at the completion of the trial. Patients will be asked to return all unused investigational drug at each visit. The investigational drug should be dispensed by the Investigator, or by a qualified individual under the Investigator's supervision. An up-to-date treatment inventory/dispensing record must be maintained as described in Section 10.3.

Overall trial non-compliance is defined as taking less than 80% or more than 120% of investigational drug during the entire treatment period. Patients will record missed doses in a diary that will be reviewed at every visit by site staff and the site monitor. Patients exhibiting poor compliance as assessed by investigational drug counts (2 or more missed investigational drug days in 1 week) should be counseled on the importance of good compliance to the trial dosing regimen. Patients who are persistently non-compliant (< 80% or > 120%) should be discussed with the Medical Monitor to determine whether they should be withdrawn from the trial.

9.7. Randomization and Blinding

This is an open-label trial; there is no randomization or blinding.

10. INVESTIGATIONAL DRUG MATERIALS AND MANAGEMENT

10.1. Investigational Drug

RPC1063 will be provided as powder-filled capsules. RPC1063 drug substance is [REDACTED]. Two RPC1063 dosage strengths have been prepared for the clinical investigations; 0.25 mg (size 4 capsule) and 1 mg (size 4 capsule).

RPC1063 capsules will be manufactured, quality control tested and released in accordance with good manufacturing practices.

All investigational drug must be stored in a secure location.

10.2. Packaging and Labeling

RPC1063 capsules will be packaged in 30 cc white high-density polyethylene bottles (35 capsules per treatment bottle; 12 capsules per dose escalation bottle), closed with a 28 mm child resistant screw-cap that is induction sealed.

The labeling of investigational drug will be in accordance with GMP and Good Clinical Practice (GCP) and any other local regulatory requirements.

10.3. Investigational Drug Accountability

Investigational drug should not be used for purposes other than as defined in this protocol.

All supplies of investigational drug will be accounted for in accordance with GCP. There will be an individual investigational drug accountability record for each patient and the Investigator should maintain accurate records of the disposition of all investigational drug supplies received during the trial. These records should include the amounts and dates clinical drug supplies were received, dispensed to the patient, returned by the patient and returned to the Sponsor. If errors or damages in the clinical drug supply shipments occur, the Investigator should contact the clinical supply distribution vendor and the site monitor immediately. Each Investigator will provide copies of the investigational drug accountability records for inclusion in the Trial Master File after database lock. The site monitor will periodically check the supplies of investigational drug held by the Investigator or pharmacist to verify accountability of all medication used.

The Investigator will provide the investigational drug only to the identified patients of this trial, according to the procedures described in this trial protocol. After the end of the trial, the Site Monitor will perform final accountability, package, seal, and prepare for shipment.

Investigational drug and all investigational drug containers will be returned to the clinical supply distribution vendor and documentation will be returned to the Sponsor and/or designee. The Sponsor and/or designee will verify that a final report of drug accountability is prepared and maintained in the Investigator's Trial Master File.

11. EFFICACY ASSESSMENTS

11.1. Magnetic Resonance Imaging (MRI)

Brain MRIs will be acquired with and without gadolinium (Gd). The same MRI protocol will be used across all sites. To ensure quality data and standardization, the same machine and software should be used throughout the trial. MRIs for MS lesions will be read at a centralized reading facility.

Total number of Gd-enhancing (GdE) lesions, number of new or enlarging hyperintense T2-weighted lesions, lesion volume (T2-weighted images), volume of unenhancing T1-weighted lesions and brain volume (ie, brain atrophy) will be collected and reported.

The baseline MRI scans for patients from the Phase 3 parent trials (RPC01-201 and RPC01-301) will be read locally only for non-MS pathology to avoid potential unblinding of treatment assignments in the parent trials. Post-baseline MRI scans for these patients and all MRIs for patients from the RPC01-1001 parent trial will be read locally for non-MS pathology, and due to the open-label design of this trial, may be used by the Investigators to monitor MS disease activity.

MRI scans should not be performed until 30 days after the last dose of methylprednisolone treatment for relapse. Previously scheduled MRIs should be rescheduled as necessary if a relapse occurs.

11.2. Expanded Disability Status Scale and Neurological Examination

The EDSS is a standardized method, widely accepted, numerical scale used to evaluate disability in people with MS ([Kurtzke 1983](#)). The EDSS is evaluated according to signs and symptoms observed during a standard neurological examination. These clinical observations are classified in 7 FS scales, each of them grading signs and symptoms for different neurological functions: pyramidal, cerebellar, brainstem, sensory, bowel or bladder, visual, and cerebral.

The trial requires that the same evaluator performs all EDSS assessments for an individual patient when possible. In addition, EDSS raters will be a neurologist or other health care practitioner who was certified using the Neurostatus Standardized Examination and Assessment prior to trial initiation and examiners will be re-certified every 2 years throughout the conduct of the trial.

11.3. Relapse Assessment

A relapse is defined as the occurrence of new or worsening neurological symptoms attributable to MS and immediately preceded by a relatively stable or improving neurological state of at least 30 days. The new or worsening neurological symptoms must be accompanied by objective neurological worsening consistent with an increase of at least half a point on the EDSS, or 2 points on one of the appropriate FS scores, or 1 point on two or more of the appropriate FS scores compared to last rating (EDSS or FS scores) that did not occur during a relapse. The change must be documented by the evaluator at either scheduled or unscheduled visits and must affect the FS scales that correspond to the patient's symptoms (eg, pyramidal, cerebellar, brainstem, sensory, bowel or bladder, visual, or cerebral). Symptoms must persist for > 24 hours

and should not be attributable to confounding clinical factors (eg, fever, infection, injury, adverse reactions to concomitant medications). When a patient experiences new or worsening symptoms at any time prior to the 90-Day Safety Follow-up Visit that may indicate a possible relapse, he/she should telephone the treating Investigator within 48 hours of symptoms onset. The treating Investigator (or designee) will conduct a telephone questionnaire and, as necessary, will arrange an Unscheduled Relapse Visit. The visit is to be planned as soon as possible, ideally within 7 days of symptom onset.

11.4. Multiple Sclerosis Disability Progression

MS disability progression is defined as a sustained worsening in EDSS of 1.0 points or more from baseline, confirmed after a 3-month and 6-month period. Confirmation of MS disability progression must not occur at the time of a relapse. If the patient is scheduled to be evaluated to confirm their disability at the time of a relapse, the disability event must be assessed at a later visit, which may be the next scheduled visit, or an unscheduled visit conducted after the relapse has resolved. In case of MS disability progression the treating Investigator will discuss with the patient the treatment alternatives outside of the study.

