For patients from RPC01-1001, the RPC01-3001 informed consent process may begin on the last day of dosing in RPC01-1001. For the same patients, Baseline (Day 1) brain MRI, OCT, and pulmonary function tests are not required to occur on the same day; these may be performed at any time between signing informed consent and first dose of RPC1063 in RPC01-3001. The RPC01-1001 End of Study assessments and the RPC01-3001 Baseline procedures may be performed on the same day. The first dose of RPC1063 in RPC01-3001 may only be administered after completion of all RPC01-1001 End of Study assessments and all RPC01-3001 Baseline assessments.

If a patient experiences a relapse after completing a parent trial, but prior to entering RPC01-3001, the patient may remain eligible for RPC01-3001. There is no minimum waiting period following the relapse; however, the Investigator should confirm that the patient is neurologically and medically stable prior to initiating investigational drug. If the Investigator suspects the patient may require more than 14 days after the last dose of investigational drug in the parent trial to become stable, the Investigator should discuss this immediately with the Sponsor's representative to determine ongoing eligibility.

Patients will be evaluated for relapses throughout the trial, including during the Safety Follow-up Visit, and patients will be instructed to contact the treating Investigator for any new or worsening neurological symptoms during the trial that may indicate a possible relapse. If the Investigator suspects a possible relapse, an unscheduled visit is to be planned as soon as possible, ideally within 7 days of symptom onset. A relapse is defined as the occurrence of new or worsening

neurological symptoms attributable to MS and immediately preceded by a relatively stable or improving neurological state of at least 30 days.

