Procedure	Baseline (Day 1)^a	Every 3/6 Months^p (± 10 days)	Every 12 Months (± 10 days)	Unscheduled Relapse Visit^b	End of Treatment/ Early Term^c	ALC Follow- up Visit^c (every 14 days after last dose ± 3 days)	Safety Follow- up Visit^q (28 days after last dose ± 7 days)	Safety Follow- up Visit^{m, q} (90 days after last dose ± 10 days)
Brain MRI ⁿ	X ⁱ		X		X			
EDSS and neurological examination	X ^a	X	X	X	X			
MSFC and LCLA	X ^a		X	X	X			
MSQOL-54	X ^a		X		X			
Pulmonary function tests ^j	X ^a		X		X			
OCT ^k	X ^a		X		X			
Dermatological (skin) examination	X ^a		X		X			
Columbia-Suicide Severity Rating Scale (C-SSRS)	X ^a	X	X	X	X		X	X
Prior/concomitant therapy	X	X	X	X	X		X	X
AEs/SAEs	X	X	X	X	X		X	X
PK Sampling					X ^o		X ^o	X ^o
Blood Sample ^r	A blood sample will be collected at the patient's next visit after this amendment is implemented, every 6 months thereafter, and at the end of treatment for potential measurements of immune response (eg, SARS-CoV-2 serology).							

Confidential and Proprietary

Footnotes are provided on the next page.

- ^a Perform specified procedures at Baseline (Day 1) only if they were not performed at the end of treatment/study visit of the parent trial or not within the timeframe prior to the end of treatment/study visit specified by the parent trial protocol. Perform a urine pregnancy test at Baseline if more than 1 month has elapsed from the last pregnancy test in the parent trial. Approval from the Sponsor's representative is required for enrollment more than 14 days after the patient's last dose of investigational drug in the parent trial, and the patient must undergo RPC1063 dose escalation. For patients from RPC01-1001, the RPC01-3001 informed consent process may begin on the last day of dosing in RPC01-1001. For the same patients, Baseline (Day 1) brain MRI, OCT, and pulmonary function tests are not required to occur on the same day; these may be performed at any time between signing informed consent and first dose of RPC1063 in RPC01-3001. The RPC01-1001 End of Study assessments and the RPC01-3001 Baseline procedures may be performed on the same day.

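### The EDSS Baseline is not reset after a relapse between the parent trial and Day 1, so a lasting deficit from that relapse can count as confirmed progression on ozanimod in a small number of patients

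*Combined protocol and SAP*

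**What the plan says.** All references are to the combined protocol and SAP.

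- **Progression (11.4).** "MS disability progression is defined as a sustained worsening in EDSS of 1.0 points or more from baseline". The worsening has to be seen again 3 months and 6 months later. The only guard against relapse is on that confirming assessment: "Confirmation of MS disability progression must not occur at the time of a relapse".
- **Source of the Baseline EDSS (Table 2, footnote a).** The Baseline EDSS cell carries this footnote: "Perform specified procedures at Baseline (Day 1) only if they were not performed at the end of treatment/study visit of the parent trial". A further clause refers to a time window set by the parent protocol. No exception is made for a relapse after that visit. A gap of more than 14 days from the last parent dose needs Sponsor approval and dose escalation, but no new EDSS. No maximum gap is stated.
- **Relapse in the gap (7.1, 9.4).** A relapse between the two trials does not by itself bar entry. On timing, 7.1 says: "There is no minimum waiting period following the relapse". The safeguard it offers is a clinical check, in that "the Investigator should confirm that the patient is neurologically and medically stable prior to initiating investigational drug". Where stabilising may take the patient past 14 days from the last parent dose, eligibility has to be discussed with the Sponsor's representative. Section 9.4 allows the steroid regimen for this relapse.
- **Relapse definition (11.3).** Worsening is judged "compared to last rating (EDSS or FS scores) that did not occur during a relapse".
- **Analysis (13.3.3).** Time to progression is analysed by Kaplan-Meier, separately for 3-month and 6-month confirmation, with the median and its 95% CI. No rule covers a relapse before Baseline.

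**The concern.** The protocol foresees a relapse between the two trials, admits the patient and allows treatment, but does not say what happens to the reference score. The change from Baseline in such a patient can therefore include a deficit acquired before the first extension dose. In a single-arm trial no comparison group offsets this.

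Other parts of the protocol do protect the reference. Section 11.3 requires a relapse-free comparator for relapses. Table 2 gives the Baseline MRI its own repeat rule (footnote i) and the pregnancy test another (footnote a). The EDSS Baseline has no comparable safeguard. At stake is the interpretation of the two confirmed-progression curves, which serve the secondary objective of long-term efficacy.

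**Working it through.** The plan gives no figure to reproduce here, so the check has two parts: the rules applied to example patients, and a rough size.

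**Rules applied (EDSS values are illustrative assumptions)**

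1. *Parent rating carried forward.* Parent EDSS 2.0; a gap relapse leaves a lasting 3.0. At Month 3 the change is 3.0 − 2.0 = +1.0. It is still +1.0 at Month 6 (3-month confirmation) and Month 9 (6-month confirmation). Both endpoints record a progression although nothing worsened on the extension drug.
2. *Day 1 rating made during recovery.* Day 1 EDSS 4.0, recovery to 2.5, later true worsening to 3.5. From Baseline the change is 3.5 − 4.0 = −0.5, so it is not counted. From the recovered level it is 3.5 − 2.5 = +1.0, which would qualify if sustained.
3. *Relapse endpoint.* Until the next non-relapse rating, normally Month 3, the comparator in 11.3 can be the pre-relapse score. A residual of 0.5 point would then already meet the EDSS part of the definition. The event must still bring new or worsening symptoms lasting more than 24 hours, follow at least 30 stable or improving days, and match the affected functional systems. The threshold for a genuinely new event is lower, but the gap relapse is not itself counted.

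The baseline neurological examination in 12.1.1 does not close the gap. It belongs to the physical examination, which also carries footnote a in Table 2.

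**Size**

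Inputs: N = 2350 (7.1, described there as the approximate number who may be eligible). Assumed, because the documents give none of these: the same gap for every patient, a relapse rate of 0.1 to 0.4 per year, and a lasting residual of at least 1.0 point in 10% to 30% of gap relapses.

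Gap relapses = N × gap days / 365.25 × rate. False progressions = gap relapses × residual share.

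| Gap | Patient-years | Gap relapses (0.1 to 0.4 per year) | False progressions (10% of the low count to 30% of the high count) |
|---|---|---|---|
| 1 day | 2350 × 1 / 365.25 = 6.4 | 0.6 to 2.6 | 0.1 to 0.8 |
| 14 days | 2350 × 14 / 365.25 = 90.1 | 9.0 to 36.0 | 0.9 to 10.8 |
| 30 days | 2350 × 30 / 365.25 = 193.0 | 19.3 to 77.2 | 1.9 to 23.2 |

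At 14 days the upper end is 10.8 / 2350 = 0.46% of patients. The 30-day row shows sensitivity only, since entry beyond 14 days from the last parent dose needs approval.

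**The case against.** **What stands**

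- The Investigator must confirm neurological and medical stability, and a long recovery triggers an eligibility discussion. This makes a relapse-inflated Day 1 rating less likely. It does not repair a pre-relapse Baseline, because a stable residual deficit is what produces the false event and no new EDSS is required.
- Confirmation at 3 and 6 months removes transient deficits. Only a lasting residual matters.
- A 14-day gap for everyone is an upper-end case. Fourteen days is the limit without approval, counted from last dose, whereas the window that matters runs from the parent EDSS to the first extension dose. Same-day transition is allowed for RPC01-1001 patients and for Part A patients of RPC01-201 who need neither dose escalation nor cardiac monitoring.
- The endpoint is secondary and descriptive, no hypothesis is tested, and a few early events will hardly move a median.
- The parent protocols and a separate SAP are not in the text reviewed. Section 11.5 refers to a SAP, so a rule there cannot be excluded.

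**Stronger readings the documents do not support**

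- A reader might infer that the relapse rate counts the pre-dose relapse. It does not: 11.3 requires new or worsening symptoms after at least 30 stable or improving days.
- A reader might express the false events as a large share of Month 3 progressions. That needs the number of true onsets at Month 3, which the documents do not give.
- A reader might place every false event at the first post-baseline visit. Most would fall early, but a 0.5-point residual followed by a further 0.5-point change crosses the threshold later.

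**Conclusion.** The gap is real under the rules as written. A lasting residual of 1.0 point or more from a relapse before Day 1 counts as confirmed progression on ozanimod. Less often, a Day 1 rating during recovery masks later worsening. The relapse endpoint is touched only through the temporarily lower EDSS threshold.

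The likely effect is small: about 1 to 11 false progressions in the upper-end 14-day case, and fewer than one with a 1-day gap. These counts depend wholly on the assumed relapse rates, residual shares and uniform gap. The masking route was not sized. This is a worthwhile clarification of a secondary descriptive analysis and does not threaten the trial's main conclusions.

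**What to change.** In 11.4 and 13.3.3, or in the SAP before database lock:

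1. Flag every patient with relapse onset between the parent EDSS used as Baseline and the first extension dose, and report how many there are.
2. For these patients, take as the progression reference the last pre-dose EDSS made after that relapse and outside it, where one exists. Where none exists, keep the planned Baseline and the flag. State how being outside the relapse is judged.
3. Report time to 3-month and to 6-month confirmed progression with and without the flagged patients.
4. Use the first non-relapse on-study EDSS as the reference only in a sensitivity analysis. It is a post-dose reference and would absorb real worsening between Day 1 and that visit, so it should not be the main rule.

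A new Day 1 assessment rule is probably moot, since 5.2.2 says that all parent trials are complete. The cost is a little more analysis work. In these few patients a true early progression may be left out of the analysis without flagged patients, or dated later in the sensitivity analysis.
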